6.3.2.2 Dose-limiting toxicities (Cohort 3b only)

DLT is defined as a clinically significant adverse event or abnormal laboratory value assessed as unrelated to disease progression, undercurrent illness, or concomitant medications and occurring during the first 4 weeks of treatment with the combination of vemurafenib and cetuximab.

For the purposes of this protocol, the following adverse events determined to be possibly, probably or definitely related to the combination of cetuximab and vemurafenib that occur during the 28 days following the first administration of the combination of vemurafenib and cetuximab at any dose level and that meet any of the following criteria are considered to be dose-limiting toxicities (DLT) that count for the determination of the MTD.

Toxicity grades are defined in the NCI CTCAE v 4.0 ([80](#)).

- Grade ≥ 3 non-haematological toxicity (other than untreated nausea, vomiting and diarrhoea and excluding alopecia)
- Grade ≥ 3 nausea, vomiting or diarrhoea refractory to appropriate treatment for at least 2 days
- Grade 4 anaemia lasting > 7 consecutive days
- Neutropenia Grade 4 lasting > 7 consecutive days
- Neutropenia Grade 3 or 4 complicated by fever and/or infection (ANC $<1.0 \times 10^9/L$; fever $\geq 38.5^\circ C$)
- Grade 4 thrombocytopenia lasting > 7 consecutive days
- Treatment delay >33% of the scheduled doses over 28 days due to treatment related toxicity

Skin and subcutaneous tissue toxicity is not considered a DLT unless a dose reduction of study treatment is required to permit continuous dosing.

6.3.3 Dose Modifications, Interruptions, and Delays for Vemurafenib and Cetuximab (Cohort 3b only)

For all patients in Cohort 3b when an occurring toxicity can be clearly ascribed to either cetuximab or vemurafenib, it will be considered to only dose reduce the compound responsible for the toxicity. See [Table 13](#) for the recommended cetuximab dose interruptions/ modifications and [Section 6.2.1](#) for vemurafenib dose reductions.

When an occurring toxicity cannot be clearly ascribed to either cetuximab or vemurafenib, both drugs will be dose reduced as per guidance in [Table 11](#) and [Table 13](#) for vemurafenib and cetuximab respectively.

Table 13:
Dose Interruption/Modification Criteria for Cetuximab

Toxicity Grade (CTCAE, v4.0) ^a	Cetuximab dose changes during current treatment period	Dose adjustments for resumption of treatment of weekly dose
Grade 1	100% of starting dosage	100% of starting weekly dosage
Tolerable Grade 2	100% of starting dosage	100% of starting weekly dosage
Intolerable Grade 2		
First appearance	Interrupt until resolved to Grade 0 – 1	Reduce to 75% of starting weekly dosage
Second appearance	Interrupt until resolved to Grade 0 – 1	Reduce to 75% of starting weekly dosage
Third appearance	Discontinue permanently	-
Grade 3 ^b		
First appearance	Interrupt until resolved to Grade 0 – 1	Reduce to 75% of starting weekly dosage
Second appearance	Interrupt until resolved to Grade 0 – 1	Reduce to 50% of starting weekly dosage
Third appearance	Discontinue permanently	-
Grade 4		
First appearance	Discontinue permanently or interrupt until resolved to Grade 0 – 1	Reduce to 50% of starting weekly dosage
Second appearance	Discontinue permanently	-

a. Common Terminology Criteria for Adverse Events, Version 4.0.

b. Treatment interruptions or and/or dose reductions for Grade 3 haematology test abnormalities, except for neutropenia and thrombocytopenia, will be at investigator's discretion.

When an occurring toxicity can be clearly ascribed to either cetuximab or vemurafenib, it will be considered to only dose reduce the compound responsible for the toxicity (see [Section 6.2.1](#) for vemurafenib dose reductions). When an occurring toxicity cannot be clearly ascribed to either cetuximab or vemurafenib, both drugs will be dose reduced as per guidance in [Table 11](#) and [Table 13](#) for vemurafenib and cetuximab respectively.

Cetuximab infusion-related reactions - Reduce the infusion rate by 50% for NCI-CTC Grade 1 or 2 and non-serious NCI-CTC Grades 3-4 infusion related reactions. Immediately and permanently discontinue cetuximab for serious infusion related reactions, requiring medical intervention and/or hospitalization. See cetuximab SPC for further details ([79](#)).

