6.2.1 Dose Modifications, Interruptions, and Delays for Vemurafenib

Management of symptomatic adverse drug reactions (e.g., arthralgia, fatigue, rash) may require temporary interruption and/or dose reduction of vemurafenib treatment. When needed, dose reduction in 240-mg b.i.d. increments is recommended based on individual safety and tolerability. Up to two dose reductions of vemurafenib will be allowed, i.e., to 720 mg p.o. b.i.d., and then to 480 mg p.o. b.i.d. There will be no dosage reductions or interruptions for skin cancer.

Dose escalation after dose reduction is generally not recommended unless under special circumstances, i.e., increased likelihood of clinical benefit for the dose increase and no safety concerns. This should only be done after discussion with the Sponsor. Dose increases above 960 mg b.i.d. are NOT allowed.

Patients with ECD/LCH have the option of discontinuing vemurafenib treatment after one year, if the investigator considers it to be in the best interest of the patient. Patients can then resume vemurafenib treatment if they become symptomatic or if their scans show worsening of their disease.

Dosage modification criteria should occur as follows (also see Table 11):

**Table 11:
Dose Interruption/Modification Criteria for Vemurafenib**

Toxicity Grade (CTCAE, v4.0) ^a	Vemurafenib dose changes during current treatment period	Dose adjustments for resumption of treatment
Grade 1	100% of starting dosage	100% of starting dosage
Tolerable Grade 2	100% of starting dosage	100% of starting dosage
Intolerable Grade 2		
First appearance	Interrupt until resolved to Grade 0 – 1	Reduce by 240 mg b.i.d.
Second appearance	Interrupt until resolved to Grade 0 – 1	Reduce by 240 mg b.i.d.

Toxicity Grade (CTCAE, v4.0) ^a	Vemurafenib dose changes during current treatment period	Dose adjustments for resumption of treatment
Third appearance	Discontinue permanently	
Grade 3 ^b		
First appearance	Interrupt until resolved to Grade 0 – 1	Reduce by 240 mg b.i.d.
Second appearance	Interrupt until resolved to Grade 0 – 1	Reduce by 240 mg b.i.d.
Third appearance	Discontinue permanently	–
Grade 4		
First appearance	Discontinue permanently or interrupt until resolved to Grade 0 – 1 ^c	Reduce to 50% of starting dosage or reduce to 480 mg b.i.d. if starting dose is 720 mg b.i.d.
Second appearance	Discontinue permanently	–

a. Common Terminology Criteria for Adverse Events, Version 4.0.

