b. Treatment interruptions or and/or dose reductions for Grade 3 haematology test abnormalities, except for neutropenia and thrombocytopenia, will be at investigator's discretion.

c. Discontinue permanently if starting dose is 480 mg b.i.d.

Prolongation of the corrected QT (QTc) interval (change from baseline) was observed in a substudy of the NP22657/BRIM-2 phase II trial. As a result of these findings, the following recommendations have been developed to minimize the risk of ventricular arrhythmia in patients with metastatic melanoma treated with vemurafenib:

Avoid combination with other agents with known potential to lead to prolongation of QTc interval, if possible.

ECG monitoring, with a focus on QTc interval, should occur during the Screening/Baseline period, 28 days after starting vemurafenib, every 28 days for the following 3 months, and every 12 weeks thereafter until study drug discontinuation at the End of Treatment Visit, and at the Safety Follow-Up Visit.

If QTc interval exceeds 500 ms or the change from baseline is > 60 ms, vemurafenib treatment should be temporarily interrupted. The Investigator should check electrolytes (K+, Mg++, and Ca++) with a focus on hypokalaemia, correct any electrolyte abnormalities prior to reinstitution of therapy, recheck concomitant medications to insure that none has been implicated in QTc prolongation, and rule out or control other cardiac risk factors (i.e., ischemia). ECG should be monitored weekly until QTc decreases to less than 500 ms, at which point treatment should be reinitiated at one reduced dose level, i.e., from 960 mg b.i.d. to 720 mg b.i.d. If a subsequent increase in QTc to > 500 ms or change from baseline is > 60 ms is observed, vemurafenib may be reduced to 480 mg b.i.d.

Vemurafenib should be permanently discontinued if a QTc increase meets both criteria of > 500 ms and > 60 ms change from pre-treatment values or if QTc > 500 ms or change from baseline > 60 ms is observed on two separate prior occasions.

If a patient's study dose has been interrupted for > 4 weeks due to an AE the patient will be considered to have discontinued from the study. However, a temporary discontinuation of drug

for up to 4 weeks is allowed in case of tumour surgery or other procedures for safety reasons or in the best patient interest, or elective procedures in the best patient interest.

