6.3.2 Recommended Dose of Vemurafenib and Cetuximab

A dose will be considered non-tolerable and dose escalation will cease if 2 or more of up to 6 evaluable patients experience a DLT at a dose level. Once the non-tolerable dose is defined the MTD will be confirmed at the previous dose-level below or a dose between the MTD and the last tolerable dose (see [Section 6.3.1](#)). Six evaluable patients are required to determine the MTD.

Expected dose levels for the dose escalation are described in [Section 6.3.1](#). The dose escalation guidelines are summarized in [Section 6.3.2.1](#). Decisions to escalate or de-escalate the doses will be made based on a review of all available safety data both from the study i.e. nature of the DLTs that occurred at one dose level together with all other available data including generally available data on vemurafenib and cetuximab.

The MTD is defined to be the highest dose of vemurafenib in combination with cetuximab which can be given to 6 patients such that less than 2 subjects experience DLT within 28 days (or no more than one-third if there are more than 6 treated patients).

The recommended dose for stage I/II will be based on considerations of the estimated MTD, and on an overall assessment of safety taking into consideration tolerability data from subsequent cycles at all different dose levels tested. The recommended dose for stage I/II will be determined once the MTD is determined by the Sponsor after discussion with the study Steering Committee. The decision to continue enrolment in Cohort 3b after the Part I dose escalation phase will be decided by the Sponsor in discussion with study Steering Committee.

Dose Escalation Guidelines (Cohort 3b only)

A minimum of 3 patients initially will be enrolled at the first dose level (Dose level 1 [Section 6.3.1](#)).

The first patient entered at the first dose level will be observed for at least 28 days before the next two patients receive vemurafenib and cetuximab at that dose level. For subsequent dose levels, three patients can be entered simultaneously, although close monitoring is required.

The dose escalation rules ([Table 12](#)) proceed as follows, escalating in cohorts of 3-6 patients per dose level.

Three patients are treated at the current dose level.

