- If at least 2 patients are observed to have a dose-limiting toxicity (DLT) (DLTs are defined in [Section 6.3.2.2](#)) during the 28 days following the first administration of vemurafenib and cetuximab (DLT assessment period), the MTD will have been exceeded and no further patients will be enrolled at this dose level or at any higher dose level. The prior dose level is defined as the MTD (unless only 3 patients have been treated at that level, in which case it is the tentative MTD).

- If 0 of the 3 patients are observed to have DLT during the DLT assessment period, the dose level is escalated one step for the next cohort of 3 patients, and the process continues as above.
- If exactly 1 of the 3 patients treated show DLT during the DLT assessment period, 3 additional patients are treated at the current dose level.

If none of these additional 3 patients show DLT during the DLT assessment period, the dose level is escalated for the next cohort of 3 patients, and the process continues as above; otherwise, the prior dose level is defined as the MTD (unless only 3 patients have been treated at that level, in which case it is the tentative MTD).

A tentative MTD becomes final when a total of 6 patients are treated with less than 2 showing DLT.

Once the MTD is determined, the dose to be recommended for stage I/II will be confirmed by the Sponsor in discussion with the study Steering Committee.

Table 12:
Dose Escalation Guidelines

Number of Patients with a DLT at a given dose level	Escalation Decision Guidance
0 out of 3	Enter 3 patients at the next dose level
1 out of 3	Enter at least 3 more patients at this dose level and then If 0 of these 3 patients experience a DLT, proceed to the next dose level. If 1 or more of these 3 patients experience a DLT then dose escalation is stopped and this dose is declared the maximal administered dose as the MTD has been exceeded. Three additional patients will be entered at the next lower dose level if only 3 patients were treated previously at that dose, or an intermediate lower dose level will be assessed
≥ 2	Dose escalation will be stopped. This dose level is declared the maximal administered dose (highest dose administered). Three additional patients will be entered at the next lower dose level if only 3 patients were treated previously at that dose, or an intermediate lower dose level will be assessed
≤ 1 out of 6 at highest dose level below the maximal administered dose	This is the MTD.

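### Read literally, the skin exemption in Section 6.3.2.2 leaves out of the DLT count a Grade 3 or worse skin reaction that ends treatment outright, while a Grade 3 rash resumed at a reduced dose is counted

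*Protocol*

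**What the plan says.** Section 6.3.2.2 lists the toxicities that count as DLTs in the dose-finding part of Cohort 3b. They include non-haematological toxicity of Grade 3 or higher, with some exclusions, and "Treatment delay >33% of the scheduled doses over 28 days due to treatment related toxicity". After the list comes a sentence on skin: "Skin and subcutaneous tissue toxicity is not considered a DLT unless a dose reduction of study treatment is required to permit continuous dosing".

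The dose-modification tables treat a dose reduction and a permanent stop as different actions. For a first Grade 3 event, Table 11 (vemurafenib) and Table 13 (cetuximab) call for interruption and then a lower dose. For a first Grade 4 event, both tables read "Discontinue permanently or interrupt until resolved to Grade 0 – 1", so a permanent stop is allowed with no earlier reduction.

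The DLT count drives the 3+3 rule in Section 6.3.2: "If 0 of the 3 patients are observed to have DLT during the DLT assessment period, the dose level is escalated one step". The maximum tolerated dose (MTD) is the highest dose that can be given to six patients "such that less than 2 subjects experience DLT within 28 days". The same section adds judgement to the count. "Decisions to escalate or de-escalate the doses will be made based on a review of all available safety data", and the dose for stage I/II also rests on "an overall assessment of safety taking into consideration tolerability data from subsequent cycles".

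**The concern.** The skin sentence has one way back into the DLT definition: a dose reduction that lets dosing go on. A patient whose skin reaction ends treatment outright has no reduction and no further dosing, so the wording does not reach that case. The order of severity is then reversed. A rash that can be managed at a lower dose is dose-limiting, and a reaction too severe to manage at any dose is not.

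At stake is the direction of the error. An uncounted event enters the 3+3 rule as a tolerated patient, so it can only favour a higher dose. The intent was probably to spare rash that can be dosed through, but the sentence does not say so.

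**Working it through.** The protocol states no figure for this point, so the check has three parts: the wording, the delay criterion and the escalation rule.

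**1. Wording: which skin events count**

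- First Grade 3 event, interrupted and resumed at a reduced dose (Tables 11 and 13): a reduction is required to keep dosing, so it is a DLT.
- First Grade 4 event, interrupted and resumed at a reduced dose: a DLT for the same reason.
- First Grade 4 event, permanent-stop option chosen: no reduction and no continued dosing, so it is not a DLT under the skin sentence.

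**2. Does the criterion for delays above 33% catch the last case?**

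Two doubts come before any arithmetic. The criterion speaks of delay, and a permanent stop is not plainly a delay. The skin sentence also follows it with no limitation, so it can be read as overriding it. Suppose both doubts are resolved in favour of counting. The criterion names no drug as denominator, so each choice is shown.

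Inputs: vemurafenib twice daily from Day 2 (Section 6.3.1); cetuximab on Day 1 and then weekly (synopsis dosing table).

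Vemurafenib, Days 2–28: 27 days × 2 = 54 doses.
- First missed dose on the morning of Day 20: 18/54 = 33.3%, just above 33%.
- First missed dose on the evening of Day 20: 17/54 = 31.5%, not met.
- First missed dose on the morning of Day 21: 16/54 = 29.6%, not met.

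Cetuximab, Days 1, 8, 15 and 22: 4 infusions.
- Day 22 missed only: 1/4 = 25%, not met.
- Days 15 and 22 missed: 2/4 = 50%, met.

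Both drugs pooled: 54 + 4 = 58 administrations.
- Stop from Day 19: (20 + 1)/58 = 36.2%, met.
- Stop from Day 20: (18 + 1)/58 = 32.8%, not met.

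Sensitivity to the window. If Day 29 is counted, there are 28 × 2 = 56 vemurafenib doses and 5 infusions. Stopping both drugs from Day 21 then misses infusions on Days 22 and 29, which is 2/5 = 40% and is caught. Stopping both from Day 23 misses 14/56 = 25% of vemurafenib and 1/5 = 20% of cetuximab, and escapes. The boundary moves by a few days but does not disappear.

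**3. Effect on the 3+3 rule**

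| Patients observed | Count as written | Count with the event included |
|---|---|---|
| First 3: one such reaction, no other DLT | 0/3, escalate | 1/3, treat 3 more |
| First 3: two such reactions, no other DLT | 0/3, escalate | 2/3, stop |
| First 3: one such reaction and one other DLT | 1/3, treat 3 more | 2/3, stop |
| After 1/3: one such reaction in the next 3 | 1/6, escalate | 2/6, stop |

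**4. How often might it happen?**

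The trial summaries in Section 1.3.5 suggest rarely under vemurafenib alone. In BRIM-2, Grade 4 rash was 0 of 132, and none of the four discontinuations for adverse events was for rash. In PLX 06-02 (87 patients), the four patients with a Grade 4 event had raised GGT (two), fatigue (one) or pancytopenia (one). The text at hand gives no rate for the combination with cetuximab.

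**The case against.** The strongest reply is that no sensible investigator would apply the sentence this way. If needing a lower dose is dose-limiting, being unable to continue at all is so with greater force. That is very likely the intent. It does not remove the defect, because a DLT definition is there so that the count does not depend on inferring intent.

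A second reply is that the count is not automatic. Table 12 is framed as guidance, and Section 6.3.2 bases escalation on all available safety data. A Grade 4 skin reaction that ended treatment in one of three patients would be prominent in that review. This stands and is the main reason the point is small. The review can hold back an escalation, but it does not reclassify the event or change the MTD definition.

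A third reply is that stops before about Day 20 exceed 33% of vemurafenib doses. That is right numerically, provided that delay includes a permanent stop and the skin sentence does not override the criterion. Late stops remain.

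A reader might want to add prolonged interruptions, on the strength of this rule in Section 6.2.1: "study dose has been interrupted for > 4 weeks due to an AE the patient will be considered to have discontinued from the study". The documents do not support that extension. An interruption of more than 4 weeks that starts after the first dose cannot become a discontinuation inside a 28-day window. The tables also make a reduced dose the condition for resuming after a first Grade 3 event, or after a first Grade 4 event managed by interruption. The required reduction is therefore arguably present from the moment of interruption, and such cases already count.

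**Conclusion.** A minor drafting defect in a safety-governing definition. As worded, a Grade 3 or worse skin reaction with onset in the 28-day window that leads directly to permanent discontinuation is not a DLT. In practice this is chiefly a first Grade 4 event where the permanent-stop option is taken. The delay criterion does not reliably catch it, especially for stops from about Day 20–21 on a Days 2–28 count.

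The consequence is confined to Cohort 3b Part 1, which Section 8.4 caps at 18 patients, and the safety review softens it. A reader might infer that the MTD is biased upward by a measurable amount, or that the recommended dose is unsafe. Neither follows. The text at hand gives no rate of treatment-ending skin reactions for the combination, and the monotherapy summaries suggest they are rare. Only the direction of the error and its effect per event can be stated.

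The conclusion rests on a literal reading of the skin sentence.

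**What to change.** Keep the sentence in Section 6.3.2.2 and add one clause at its end: *or it leads to permanent discontinuation of either study drug*. Naming either drug matters because Section 6.3.3 allows action on one drug alone.

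The cost is one clause, and slightly fewer escalations if such events occur. If Part 1 is already complete, no amendment is needed for it. Check its patients, at most 18, for skin events with onset within 28 days that led to discontinuation. The check should go by onset of the event, because the stop itself may be recorded later.

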6.4 PREPARATION AND ADMINISTRATION OF STUDY DRUGS

6.4.1 Vemurafenib

Vemurafenib will be supplied as 240-mg film-coated tablets packed in bottles for oral administration. No further preparation is required.

Upon arrival of the investigational product at the site, site personnel should check them for damage and verify proper identity, quantity, integrity of seals and temperature conditions, and report any deviations or product complaints to the monitor upon discovery.

Vemurafenib should be stored at room temperature < 25°C and should be protected from excessive exposure to sunlight. Patients will be requested to store vemurafenib at the recommended storage conditions noted on the label, out of the reach of children or other vulnerable persons. Under hot weather conditions storage in the refrigerator is possible to not exceed storage conditions above 25 °C.

For additional batch-specific instructions and information for vemurafenib film-coated tablets, please refer to the packaging.

Vemurafenib should be taken at approximately the same times each day, the first dose is to be taken in the morning and the second dose is to be taken approximately 12 hours later in the evening. Each dose should always be taken in the same manner i.e. either with or without a meal

If a patient misses a dose (e.g., due to emesis), he or she should be instructed not to take or make up that dose and to resume dosing with the next scheduled dose. Missed doses will not be made up.

